1.0 Introduction

Cancer represents a significant burden of aging. When comparing those over 65 years to those under 65, the incidence of cancer is 10 times greater, and the cancer death rate is 16 times greater.¹ Care for older adults with surgically-treated gastrointestinal (GI) or genitourinary (GU) malignancies imposes particular burdens because the treatments are highly morbid, especially in older adults with multimorbidity. For instance, pancreatic cancer is the fourth leading cause of cancer deaths with 70% of this mortality occurring in patients over 65, and nearly three-quarters of patients die within 5 years of resection.^{1,2} Surgeons face a quandary: resection is the only chance for cure, but resection potentially increases suffering.

Concurrent palliative care consultation (PCC) with oncologic care improves clinical outcomes earlier in the illness trajectory as well as at the end of life (EOL).³ PCC reduces use of intensive life-prolonging therapy at EOL while improving quality of life (QOL) and other patient-centered outcomes.^{4,5} Early PCC concurrent with chemotherapy improves survival for patients with advanced malignancies.^{4,6} **PCC also has been associated with improved surgical outcomes,⁷ yet surgeons frequently call for such expertise only as a last resort. There is a dearth of literature to help surgeons understand how PCC can benefit surgical patients with serious age-related conditions, such as abdominal malignancies.**

The Surgery for Cancer with Option of Palliative Care Expert (SCOPE) Trial is an investigation that will study the effect of a palliative care implementation during the preoperative, perioperative, and postoperative phase for older adults undergoing cancer surgery for selected (see inclusion criteria) abdominal malignancies. SCOPE will be a single-blind, single-institution randomized controlled trial of 236 patients. Intervention arm patients will receive a preoperative outpatient specialty palliative care consultation from a palliative care provider (physician or nurse practitioner) in addition to inpatient and outpatient palliative care follow-up postoperatively. Control arm patients will receive usual care with PCC available at the discretion of the primary treatment team (currently these patients rarely get PCC and usually only in the last weeks of life). **The central hypothesis of the SCOPE Trial is that preoperative, perioperative, and postoperative specialty PCC will improve patient functioning and quality of life while decreasing intensive life-prolonging therapy at EOL in patients undergoing resection of selected abdominal malignancies.**

Specific Aims

Aim 1: To determine whether preoperative, perioperative, and postoperative specialty palliative care consultation improves 90 day post-operative functional status. We hypothesize that PCC will improve physical and functional quality of life as measured by the Trial Outcome Index (TOI) of the FACT-G instrument in patients undergoing resection. The SCOPE Trial's primary end-point will be TOI at approximately 90 days postoperatively, controlling for baseline score. Secondary end-points will be QOL (FACT-G) at approximately 90 days and days alive at home during the first 90 days. Exploratory endpoints will be anxiety, and depression (PROMIS Anxiety-6 and Depression-6) and Karnofsky performance status at 90 days; satisfaction with hospital stay; and initiation of appropriate adjuvant therapy.

Aim 2: To determine whether preoperative, perioperative, and postoperative specialty palliative care consultation improves cancer survivorship. We hypothesize that PCC will improve the length and quality of life for patients undergoing resection. Secondary outcomes for

Aim 2 are overall survival at three years and post-traumatic stress disorder symptoms at 180 days. Exploratory endpoints include healthcare utilization, post-traumatic growth, and physical functioning at approximately 180 days post-operatively; long term trends in physical functioning, QOL, size of life space, employment, health care utilization, long-term facility placement, and caregiver burden.

Aim 3: To determine whether preoperative, perioperative, and postoperative specialty palliative care consultation affects quality of EOL care after resection. We hypothesize that preoperative and ongoing PCC will improve quality of EOL care. To test this hypothesis, we will analyze patients who die during the SCOPE Trial. Outcomes for this subgroup analysis will be receipt of ineffective and burdensome treatment (chemotherapy within 14 days of death) or delayed referral to hospice (length of stay in hospice less than 7 days), days at home without an ER visit in last 30 days of life, location of death, and quality of death and dying as measured by the FATE-S instrument.

To accomplish these Aims, my team will randomize 236 patients at Vanderbilt University's surgery, urology, and gynecology clinics to complete the SCOPE Trial with 118 patients in each arm. A positive effect of PCC in any of the Aims would indicate early PCC is novel strategy to improve clinical care in these surgical patients. Any negative results will be investigated using multivariate analyses on covariates to identify subpopulations (such as frail patients) in which the intervention was more effective as a basis for designing future studies of the effects of PCC on surgical patients with serious age-related conditions.

2.0 Background

End-of-life (EOL) care in the United States is extremely expensive and often fails to deliver comfort and dignity. Care in the last year of life consumes over 25% of Medicare expenditures.⁸ Most people desire to die at home, but only about a third do so, and a quarter die as inpatients in hospitals.^{9,10} Hospice care, in which patients with terminal illnesses forego life-prolonging care and instead receive intensive comfort focused care with an aim of remaining at home as long as possible, is one means to address these shortcomings in EOL care.¹¹ However, fewer than half of patients receive hospice care at the time of death, and almost 30% of patients who enroll in hospice do so within three days of death and so have very little time to benefit from hospice.¹⁰

One strategy to address these issues is involvement of palliative care specialists earlier in the course of life-limiting illnesses. Palliative care providers specialize in helping patients articulate the goals for their care and in determining when medical interventions are consistent with these goals. When involved early in the course of treatment, palliative care specialists guide patients through their treatment and allow patients and providers to recognize the point when aggressive life-prolonging care no longer meets the patient's goals. Early palliative care interventions accordingly have both decreased intensity of EOL care and increased hospice enrollment and the duration of time under hospice care.^{4,13}

Palliative care providers also specialize in alleviating physical symptoms and psychosocial distress brought by life-threatening illnesses. Thus, the early initiation of palliative care has been shown to bring benefits beyond improving EOL care: interventions involving early initiation of palliative care have improved patient-centered outcomes including physical functioning, quality of life, satisfaction, and symptom burden.^{4,5,12-15} Moreover, in patients with

advanced cancer, randomized controlled trials have shown a survival advantage in patients who receive palliative care interventions early in the course of their treatment.^{4,6}

Early palliative care consultation has the potential to lengthen life, improve patient-centered outcomes, increase quality of EOL care, and reduce unnecessary expenses associated with inappropriately aggressive EOL care. Patients with incurable metastatic cancer are one population where palliative care has been shown to have such positive effects, but there are likely other populations for whom palliative care could provide similar benefits, including surgical patients with serious age-related conditions, like cancer.

There is a driving, unmet need to determine what surgical patients with age-related conditions would benefit from early palliative care. A recent expert panel convened by the National Institutes of Health and the National Palliative Care Research Center identified a need to develop clinical trials to test the effectiveness of early specialist palliative care consultation in surgery patients.¹⁶ The SCOPE Trial will address this research priority and determine whether patients undergoing resection for **poor-prognosis abdominal malignancies** constitute another group for whom early palliative care will yield improvements in care.

3.0 Preliminary Studies

Previous research on early initiation of palliative care has occurred mostly in the setting of incurable diseases—typically metastatic cancer or end-stage heart failure. Only one trial has examined the initiation of early palliative care in surgical patients, and this trial examined only outcomes related to quality of life and symptom burden without looking at effects on surgical or oncologic outcomes or EOL care.¹⁷ Moreover, the patients involved in that study were patients with advanced malignancy undergoing any surgical procedure, not necessarily the potentially curative resections to be examined in the SCOPE Trial. The only trial to examine the impact of early palliative care along with potentially curative therapy was a recently reported trial in bone marrow transplant patients.¹⁸ The SCOPE Trial is novel as the population is both a surgical population and a population undergoing potentially curative therapy.

Another burgeoning area of research is the pre-operative optimization of surgical patients to improve outcomes and reduce complications, especially in surgical patients with age-related conditions. Most research has focused on encouraging physical prehabilitation to improve patient functional status before the operation, eliminating modifiable risk factors (such as smoking), or controlling comorbidities (such as diabetes).¹⁹⁻²¹ Preoperative palliative care is thus a novel preoperative intervention that may alleviate symptom burden and psychosocial distress, both of which could impair the resilience of patients to withstand the stresses of an operation.^{22,23}

A third important growing area of research is cancer survivorship, especially in older patients. A recent expert conference convened by the National Institute on Aging and the National Cancer Institute identified a research priority of investigating interventions to improve health and functioning of older patients undergoing treatment for cancer.²⁴ The SCOPE Trial offers the opportunity to address this recently identified research priority by examining the effect of early palliative care on survivorship after surgery for cancer.

Studying the benefits of preoperatively initiated palliative care for patients undergoing resection of GI and GU malignancies thus would ride the crest of three waves of research—research into early palliative care interventions, research into preoperative interventions to improve surgical outcomes, and research on interventions to improve cancer survivorship. At the same time as it fits into these young but robust areas of research, the SCOPE Trial also fills voids in these bodies of investigation by using a novel intervention with a novel population.

The SCOPE Trial will investigate a new strategy of preoperative, perioperative, and postoperative PCC, which can improve patient reported and clinical outcomes while promoting patient-centered care. This investigation could offer hope for patients by reducing suffering and improving their clinical recovery. Preoperative PCC could then be applied to different surgical populations with serious age-related conditions, such as frailty and organ failure.

4.0 Study Objectives and Endpoints

4.1 Study Objectives. The primary objective of the SCOPE trial is to determine whether a palliative care intervention improves recovery and quality of life after major abdominal operations for cancer. Secondary objectives are to determine whether the palliative care intervention improves long-term functioning and quality of life for these patients and whether the palliative care intervention improves EOL care for the subset of patients who die during the study.

4.2 Efficacy Endpoints

4.2.1 Primary Endpoint. The trial's primary endpoint will be score on the FACT-G TOI at 90 days post-operatively (controlling for baseline score).

4.2.2 Secondary Endpoints

- [1] FACT-G score at 90 days
- [2] Days alive at home during first 90 days
- [3] PTSD Checklist-Civilian Version score at 180 days
- [4] Overall survival at 1 year

4.2.3 Exploratory Endpoints

- [1] FACT-G TOI score [180 days, trend over study period]
- [2] FACT-G score [180 days, trend over study period]
- [3] PROMIS Anxiety-6 score [90 days, 180 days]
- [4] PROMIS Depression-6 score [90 days, 180 days]
- [5] Satisfaction with hospital stay [30 days]
- [6] Time from surgery to adjuvant therapy
- [7] Overall Survival [3 years]
- [8] Post-traumatic Growth Inventory score [180 days]
- [9] Karnofsky Performance Status [90 days, 180 days, trend over study period]
- [10] Employment [trend over study period]
- [11] Number of hospital admissions over study period
- [12] Number of ER visits over study period
- [13] Long-term care residence [trend over study period]
- [14] Life Space Assessment Questionnaire score [trend over study period]
- [15] Zarit Burden Interview [90 days, 180 days, trend over study period]

4.2.4 Planned Subgroup Analysis: Patients who die during the course of the study will be included in a subgroup analysis with the following outcomes.

- [1] Receipt of chemotherapy within 14 days of death
- [2] Hospice enrollment of less than 7 days before death
- [3] Days at home without ER visit or hospital stay in last 30 days of life
- [4] Location of death (home vs. facility)
- [5] Quality of end-of-life care (FATE-S score)

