chi-squared tests will be used. A logistic regression model will be used for adjusted analysis to estimate the odds of receiving intensive life-prolonging therapy due to early PCC. Missing data will be imputed using a model-based imputation process. Non-linear effects of continuous variables will be fit using restricted cubic splines, and modern regression model building techniques will be used. All covariates included in the adjusted models will be selected a priori and the model complexity will be based on the general rule that a model must fit no more than $m/10$ parameters to allow for proper multivariable analysis and to be generalizable to future patients, where m is the effective sample size. Graphical techniques will be used to perform model diagnostics and evaluate assumptions. Multicollinearity will be assessed using variance inflation factors and in the event of highly collinear variables, principal component analysis will be used.

10.2 Missing Data. When data cannot be collected, we will impute missing variables via multiple imputation methods. Missing data are common due to deaths and loss to follow-up. While our team has a proven track record of achieving high follow-up we will carefully analyze whether particular baseline demographics are associated with missing evaluations of long-term testing.

10.3 Statistical Meetings. The VCC will work regularly with our statisticians at the ongoing weekly biostatistics meetings. Final analyses will occur during the last 6 months of the study period, when monitoring, quality checks, data lock, archiving and manuscript preparation will take place.

11.0 Privacy/Confidentiality Issues. Protected Health Information (PHI) will be kept confidential and shared with other investigators or regulatory bodies only when in accordance with relevant governmental and institutional policies. At no time will we reveal subject identities in any manner, whether in presentation, description or publication of the research for scientific purposes. All data obtained with subject or provider identifiers will be kept in locked file cabinets to ensure confidentiality, and all paper file contents will be shredded before disposal. All subjects will be assigned a unique study number for use in the computer database, and all electronic data will be kept in password-protected computer files to ensure confidentiality.

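### Aim 3 compares end-of-life care only among patients who die, a group that PCC is expected to change, so its result should be reported as an association and should not on its own count as an effect of PCC

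*Combined protocol and SAP*

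**What the plan says.** Aim 3 in the Introduction states a causal hypothesis: "We hypothesize that preoperative and ongoing PCC will improve quality of EOL care". The analysis set follows at once: "To test this hypothesis, we will analyze patients who die during the SCOPE Trial". Section 4.2.4 repeats that set: "Patients who die during the course of the study will be included in a subgroup analysis with the following outcomes". It lists five outcomes: late chemotherapy, short hospice enrolment, days at home in the last 30 days, location of death, and the FATE-S score.

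Aim 2 expects PCC to act on death itself: "We hypothesize that PCC will improve the length and quality of life for patients undergoing resection". Overall survival is an endpoint at 1 year (4.2.2) and at 3 years (4.2.3), and the Background cites a survival advantage from early palliative care in advanced cancer.

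Section 10.1 plans a chi-squared test for intensive therapy in the last two weeks of life. It adds a logistic model to "estimate the odds of receiving intensive life-prolonging therapy due to early PCC". Section 10.1 does not restate the analysis set, but an outcome tied to the last two weeks of life exists only for patients who died. The adjustment factors are baseline variables. On interpretation, the Introduction says: "A positive effect of PCC in any of the Aims would indicate early PCC is novel strategy".

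**The concern.** Randomisation makes the two groups of 118 comparable. It does not make the patients who later die in each group comparable if treatment affects survival. Suppose PCC prevents some deaths. The control decedents then include patients whose counterparts in the PCC arm are alive and outside the analysis. If those patients would have had more, or less, burdensome care at the end of life than the other decedents, the arms differ even when PCC does nothing to that care. A shift in the timing of death can act in the same way, for example because a patient who dies soon after surgery has little time to enrol in hospice.

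What is at stake is the reading of Aim 3. The trial's own survival hypothesis, if true, undermines the causal reading of its end-of-life comparison. No section acknowledges this, defines what is being estimated among decedents, plans a sensitivity analysis, or defines an end-of-life outcome over all randomised patients.

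**Working it through.** **The plan's own figures.** Section 10.1 gives 98 evaluable and 118 enrolled per group for the primary endpoint. A two-sided 5% test with SD 18.1 and a difference of 7.28 needs 98 per group for 80% power. Allowing for 15% loss, 98/0.85 = 116, close to the stated 118. These figures matter here only because 118 is the denominator per arm. No number of deaths, event rate or power is stated for Aim 3, so every input below other than 118 is an assumption.

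**Check 1: PCC prevents some deaths and has no effect on end-of-life care in any patient.**

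- Control 3-year mortality p_C is 30%, 45% or 60%. The hazard ratio (HR) for death is 1.0, 0.85 or 0.70.
- PCC mortality: p_T = 1 − (1 − p_C)^HR.
- Share of control decedents who would have survived under PCC: s = 1 − p_T/p_C.
- End-of-life event rate: 30% in patients who die under either arm; 10%, 50% or 60% in those saved by PCC.
- False difference (PCC minus control) = 0.30 − [(1 − s) × 0.30 + s × q], where q is the rate in those saved.

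Worked case: p_C = 0.45, HR = 0.70, q = 0.60.

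- p_T = 1 − 0.55^0.70 = 0.342, so about 53 control and 40 PCC deaths.
- s = 1 − 0.342/0.45 = 0.240.
- Control decedent rate = 0.760 × 0.30 + 0.240 × 0.60 = 0.372, against 0.300 under PCC.
- False difference = −7.2 points. A nominal 5% chi-squared test rejects in about 11% of trials.

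| HR | s | False difference (absolute) | Chi-squared rejection |
|---|---|---|---|
| 1.0 | 0 | 0 | 5% |
| 0.85 | 10–13% | about 2–4 points | about 6–7% |
| 0.70 | 21–26% | about 4–8 points | about 7–12% |

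The sign depends on q: with q = 10% the PCC arm looks worse, and with q = 50% or 60% it looks better.

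**Check 2: one latent severity factor drives both death and end-of-life care.** In simulations of 2,000,000 patients with the same mortality range and HR 0.85 or 0.70, the false difference was 0.2 to 1.3 points (for example 39.6% against 40.9% at p_C = 0.45 and HR 0.70). A similar simulation with control mortality of 30–50% and HR 0.6–0.8 gave 0.3 to 2.1 points. The result depends on the assumed strength of the link between severity and care: varying that slope alone moved it between about 0.3 and 2.4 points.

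**Check 3: an early-death illustration, with the precision available.** Assume 40 control and 34 PCC deaths, of which 8 and 3 are early with no patient reaching 7 days of hospice. Among later deaths, 60% reach 7 days in both arms.

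- Control: 32 × 0.6 = 19.2, and 19.2/40 = 48.0%.
- PCC: 31 × 0.6 = 18.6, and 18.6/34 = 54.7%.
- Apparent gain: 6.7 points with no effect on care.
- SE = √(0.480 × 0.520/40 + 0.547 × 0.453/34) = 0.116, or 11.6 points. The bias is therefore under 0.6 SE; the Check 2 results up to 2.1 points are under 0.2 SE.

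**Check 4: the same illustration over all 118 per arm.**

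- Death without 7 days of hospice: (40 − 19.2)/118 = 20.8/118 = 17.6%, against (34 − 18.6)/118 = 15.4/118 = 13.1%.
- Death with 7 days: 19.2/118 = 16.3%, against 18.6/118 = 15.8%.

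Death with a short or absent hospice stay is lower under PCC, purely because fewer patients die. An all-randomised table would thus appear to agree with a decedent contrast that is entirely spurious.

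**The case against.** The strongest reply is that little rests on Aim 3 and the bias is probably small. Section 4.2.4 labels it a subgroup analysis, the primary endpoint is TOI alone, and section 10.1 claims no power for secondary or exploratory outcomes. Section 10.1 also calls the unadjusted comparison an association, so the causal phrase concerns one model for one outcome family. Survival is already compared by arm. Adjustment covers age, frailty and cancer type, and randomisation is stratified by cancer type. The sentence about any of the Aims is introductory text, not a formal decision rule. Finally, location of death and FATE-S exist only for decedents, so some conditioning is unavoidable.

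Most of this stands, and it limits the severity. It does not answer the point. Baseline adjustment cannot remove unmeasured determinants of death. It is also restricted by the plan's own limit of m/10 parameters: with 74 deaths that allows at most 7, and with an assumed 30% event rate (about 22 events) only 2, against six named factors of which cancer type has several levels. The subgroup label does not stop the Introduction from letting Aim 3 alone carry a conclusion.

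A reader might infer that Aim 3 will be wrong, or that a false positive is likely. The documents do not support that: they give neither mortality nor a survival hazard ratio for this cohort, and without an effect on who dies or when there is no such bias. Nor is 6.7 points an estimate for this trial. The split of 8 and 3 early deaths implies an early hazard ratio of about 0.37, the inputs have no source in the documents, and the example counts patients who never enrolled in hospice as failures, which section 4.2.4 does not settle.

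**Conclusion.** The concern holds as a matter of interpretation. Aim 3 is defined on a group formed after randomisation, the trial expects PCC to alter that group, and the plan words one of the results causally and lets it count alone towards the conclusion.

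Direction cannot be determined from the documents, and size can be given only by assumption: about 0.2 to 2 points under a single shared prognostic factor, about 2 to 8 points if the deaths PCC prevents are in patients with a very different end-of-life event rate, and zero if PCC changes neither who dies nor when. With about 40 and 34 deaths the standard error is about 12 points, so chance is the larger source of error in any single result.

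A reader might also infer that an all-randomised analysis would validate a positive Aim 3. It would not, because a pure survival benefit produces the same agreement. The primary endpoint and the survival comparison are unaffected.

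**What to change.** 1. In Aim 3 and section 4.2.4, describe the results as associations among decedents.
2. In section 10.1, replace the wording that attributes the odds to early PCC.
3. In the Introduction, amend the sentence about any of the Aims so that a positive decedent contrast alone does not count as evidence of a PCC effect.
4. Report the number of deaths and the time from surgery to death by arm beside the decedent tables.
5. For late chemotherapy and short hospice enrolment, add a supplementary table covering all 236 randomised patients. It should give, by arm, the 3-year cumulative incidence of death with the outcome and of death without it, as competing outcomes, beside overall survival. State how patients who never enrolled in hospice are counted.
6. Do not make agreement with that table a condition for accepting Aim 3.
7. Keep days at home in the last 30 days and FATE-S as descriptive results among decedents.

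No new data are needed: the Data Timeline already includes dates of death, last chemotherapy and hospice admission, and follow-up runs for three years. The cost is some wording, one extra table and a weaker Aim 3 claim. The new table mixes survival with end-of-life care, which is why overall survival must stand beside it.
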